### Schedule of Activities for Patients with DLBCL (cont.)

- n Includes systems of primary relevance (e.g., cardiovascular and respiratory systems), systems associated with symptoms (newly emergent or monitored from baseline), and areas associated with tumor assessment (lymph nodes, liver, spleen, and any other areas identified at baseline). Record new or worsened clinically significant abnormalities on the Adverse Event eCRF.
- o Unexplained fever >38°C, nightsweats, unexplained weight loss >10% of body weight over 6 months.
- p Includes hemoglobin, hematocrit, platelet count, RBC count, WBC count, and percent or absolute WBC differential count (neutrophils, eosinophils, basophils, monocytes, lymphocytes, other cells).
- q Screening laboratory assessments may be used for Day 1 of Cycle 1 if performed within 72 hours prior to Day 1 of Cycle 1.
- r Perform hematology and chemistry tests within 72 hours prior to Day 1 of each cycle, and within 24 hours prior to Days 8 and 15 of Cycle 1. Samples for exploratory biomarker research should be collected at the same time as hematology and chemistry samples.
- s Includes sodium, potassium, glucose, BUN or urea, creatinine, calculated creatinine clearance, calcium, total bilirubin, direct bilirubin, total protein, albumin, ALT, AST, alkaline phosphatase, amylase, lipase, LDH, and uric acid.
- t *Only patients treated with obinutuzumab.*
- u All women who are not postmenopausal (• 12 months of non-therapy-induced amenorrhea) or surgically sterile will have a serum pregnancy test at screening within 7 days prior to Day 1 of Cycle 1. Because of the suspected effect of idasanutlin on embryo-fetal development, monthly pregnancy testing is strongly recommended for women of childbearing potential (CTFG 2014).
- v Includes hepatitis B surface antigen, total hepatitis B core antibody, and hepatitis C virus antibody.
- w *Perform at the same time as tumor assessments at 4 months after initiation of consolidation treatment.*
- x Perform every 3 months until recovery to either normal range or baseline level, disease progression, or the start of new anti-lymphoma treatment, whichever occurs first.
- y See [Appendix 3](#) for detailed schedule.
- z Includes circulating lymphoma cells and/or cell-free circulating tumor DNA.
- aa *Perform at the same time as tumor assessments at 4 months after initiation of consolidation treatment.*
- bb Includes B-cell counts (CD19), T-cell counts (CD3, CD4, and CD8), and NK-cell counts (CD16 and CD56).
- cc Also on Day 5 of this cycle. See [Appendix 3](#) for detailed schedule.
- dd Cycle 4 Day 1 and Day 5. See [Appendix 3](#) for detailed schedule.
- ee Requires separate patient consent for RCR participation. Not applicable for a site that has not been granted approval for RCR sampling.
- ff Availability of adequate archival or freshly biopsied tumor tissue samples should be confirmed at screening (see Section [4.5.6.2](#) for details).
- gg A tumor biopsy sample is preferred and recommended at the time of progression unless no adequate tumor site is accessible.
- hh After informed consent has been obtained but prior to initiation of study treatment, only serious adverse events caused by a protocol-mandated intervention should be reported. After initiation of study treatment, all adverse events will be reported until 90 days after the last dose of study

## Appendix 2

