### 3.1.2.1 Definition of Dose-Limiting Toxicity

In this study, a DLT is defined as at least one of the following events occurring during the first cycle (*or the first two cycles in the bridging cohorts for patients with FL who start idasanutlin at Cycle 2*) of treatment and assessed by the investigator as not clearly related to the patient's underlying disease:

- *Any Grade 5 adverse event unless unequivocally due to the underlying malignancy or extraneous causes*
- Adverse event of any grade that leads to a delay of more than 14 days in the start of the next treatment cycle
- Grade 3 or 4 non-hematologic adverse event, with the following exceptions:
  - Grade 3 or 4 IRRs
    - Note that IRRs are not dose-dependent events. They may occur even after a small amount of drug has been administered.
    - Grade 3 diarrhea that responds to adequate therapy within 48 hours
    - Grade 3 nausea or vomiting that occurs in the absence of premedication and responds to adequate therapy within 72 hours
- *Any increase in hepatic transaminase > 3 • baseline and an increase in direct bilirubin > 2 • ULN, without any findings of cholestasis or jaundice or signs of hepatic dysfunction and in the absence of other contributory factors (e.g., worsening of metastatic disease or concomitant exposure to known hepatotoxic agent or of a documented infectious etiology) is suggestive of potential drug induced liver injury (according to Hy's Law) and will be considered a DLT*
- Hematologic adverse events that meet any of the following criteria:
  - Grade 3 or 4 neutropenia in the presence of sustained fever of >38°C (lasting >5 days) or a documented infection
  - Grade 4 neutropenia lasting >7 days
  - Grade 3 or 4 thrombocytopenia *if associated with Grade ≥ 3 bleeding*
  - Grade 4 thrombocytopenia lasting >7 days

Other toxicities that are considered clinically relevant and related to study treatment as determined by the investigator and the Medical Monitor may also be considered DLTs.

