**Table 2 Induction Treatment for Dose-Escalation Phase**

Dose-Escalation, FL and DLBCL Patients (28-Day Cycles): Regimen A	
Cycle 1	DLT period 
 
• Obinutuzumab 1000 mg IV on Days 1, 8, and 15
 
• Idasanutlin, oral Days 1•5, starting dose 100 mg QD, minimal clinically and pharmacologically feasible dose-escalation steps 50 mg
 

Cycles 2•6	
 
• Obinutuzumab 1000 mg IV on Day 1
 
• Idasanutlin, oral Days 1•5, starting dose 100 mg QD
 

Dose-Escalation Bridging Cohort, DLBCL Patients Only (28-Day Cycles)	
Cycle 1	DLT period 
 
• Rituximab 375 mg/m^2 IV on Day 1
 
• Idasanutlin, oral Days 1•5, starting dose MTD identified in combination with obinutuzumab with Regimen A, minimal clinically and pharmacologically feasible dose-escalation steps 50 mg
 

Cycles 2–6	
 
• Rituximab 375 mg/m^2 IV on Day 1
 
• Idasanutlin, oral Days 1•5, starting dose MTD identified in combination with obinutuzumab
 

Dose-Escalation Bridging Cohort, FL Patients Only (28-Day Cycles): Regimen B	
Cycle 1	
 
• Obinutuzumab 1000 mg IV on Days 1, 8, and 15
 

Cycles 2–6	
 
• Obinutuzumab 1000 mg IV on Day 1
 
• Idasanutlin, oral Days 1•5, starting dose MTD identified in combination with obinutuzumab with Regimen A during dose escalation, minimal clinically and pharmacologically feasible dose-escalation steps 50 mg
 

DLT period will be Cycles 1 and 2.	

*DLBCL =diffuse large B-cell lymphoma; DLT = dose-limiting toxicity; FL =follicular lymphoma; IV=intravenous; MTD =maximum tolerated dose; QD=once a day.*

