### **5.1.3 Risks Associated with Idasanutlin**

Information related to idasanutlin-associated risks is based mainly on review of data from Phase I experience in patients with solid tumors and AML (Studies NP27872, NP28902, and NP28679, respectively) as described in the Idasanutlin Investigator's Brochure. In Study NP27872 and NP28902, 160 patients with advanced malignancies (excluding leukemia) have received idasanutlin in the Phase I, entry-into-human, dose-escalation study NP27872 (99 patients) and in the Phase I DDI and relative

bioavailability study NP28902 (61 patients). Study BH29812 (idasanutlin plus obinutuzumab in R/R FL and DLBCL) had enrolled 1 patient as of 1 May 2016.

*Many of the toxicities experienced by patients with solid tumors appear to be manageable with appropriate prophylaxis, supportive therapies, and/or reversible with discontinuation of idasanutlin. Identified risks include GI disorders (diarrhea, nausea, and vomiting, myelosuppression (thrombocytopenia, neutropenia, and anemia), TLS, infectious complications, and electrolyte abnormalities. Potential risks include coagulation abnormalities and liver function test abnormalities.*

*Please refer to the current version of the Idasanutlin Investigator's Brochure for additional information on the identified and potential risks.*

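### Appendix 2 drops Cycle 1 Day 15 chemistry, though not hematology, for rituximab patients, so chemistry-based DLTs are looked for less often in the rituximab bridging cohort than in the obinutuzumab cohorts

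*Combined protocol and SAP*

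**What the plan says.** Appendix 2 (DLBCL schedule of activities) marks serum chemistry in Cycle 1 on Days 1, 8 and 15. The Day 15 cell carries footnotes r and t. Footnote r gives the sampling times: "within 72 hours prior to Day 1 of each cycle, and within 24 hours prior to Days 8 and 15 of Cycle 1". Footnote t reads "Only patients treated with obinutuzumab". The hematology row is marked for the same three days and carries no footnote t. Footnote p defines that panel: "Includes hemoglobin, hematocrit, platelet count, RBC count, WBC count, and percent or absolute WBC differential count". Footnote s lists the chemistry panel, which includes ALT, AST, total and direct bilirubin, creatinine, electrolytes, amylase and lipase.

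Table 2 gives Cycle 1 as the DLT period for DLBCL patients on idasanutlin plus rituximab. Their starting dose is the idasanutlin MTD found with obinutuzumab, and Section 3.1.2.2 allows escalation from there if safety and tolerability permit.

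Section 3.1.2.1 counts as a DLT a "Grade 3 or 4 non-hematologic adverse event, with the following exceptions", and separately "Any increase in hepatic transaminase > 3 • baseline and an increase in direct bilirubin > 2 • ULN" under stated conditions. On idasanutlin, Section 5.1.3 says: "Potential risks include coagulation abnormalities and liver function test abnormalities". It also lists electrolyte abnormalities among the identified risks.

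**The concern.** The bridging cohort asks whether the idasanutlin dose found with obinutuzumab holds with rituximab, or can be exceeded. That question is best answered when DLTs are looked for equally hard in both settings. Two kinds of DLT depend on chemistry: the transaminase-plus-direct-bilirubin criterion, and Grade 3–4 biochemical adverse events such as electrolyte, creatinine or lipase changes. For these, the rituximab cohort has one scheduled test fewer within its DLT window.

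Idasanutlin, with its stated liver and electrolyte risks, is the same drug in both cohorts, and no reason for the difference is given. An unrecorded DLT can only lower the recorded DLT rate, so any effect runs towards a higher idasanutlin dose with rituximab. In cohorts of 3 to 6 patients, a single event can change the model's recommendation.

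**Working it through.** **1. Scheduled laboratory days in Cycle 1 (Appendix 2, footnotes r and t)**

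| | Hematology | Chemistry |
|---|---|---|
| Obinutuzumab | D1, D8, D15, pre-Cycle 2 | D1, D8, D15, pre-Cycle 2 |
| Rituximab | D1, D8, D15, pre-Cycle 2 | D1, D8, pre-Cycle 2 |

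**2. Longest chemistry gap.** Cycles last 28 days, so Cycle 2 Day 1 is Day 29. With the 72-hour window, the pre-Cycle 2 sample can fall from Day 26. On nominal days:
- rituximab: 26 − 8 = 18 to 29 − 8 = 21 days
- obinutuzumab: 26 − 15 = 11 to 29 − 15 = 14 days

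The hematology gaps are the same in both.

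**3. Which DLTs are affected.** The neutropenia and thrombocytopenia criteria use counts from the hematology panel, so they are unaffected. The hepatic criterion and Grade 3–4 biochemical events need chemistry. Of these, an event still present at about Day 26 would be found by the pre-Cycle 2 sample. One present at Day 8 would be found then. Only an abnormality that arises after Day 8 and resolves before about Day 26 has no scheduled test.

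**4. What one missed DLT can do: an illustration from the Regimen A model.** Section 3.1.2.3 gives logit p(d) = log α + β·log(d/300), with log α ~ N(−1.237, 2.661) and log β ~ N(0.460, 1.816), independent. I read 2.661 and 1.816 as variances. The recommended dose minimises the expected loss

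P(p < 0.25) + 0·P(0.25–0.35) + P(0.35–0.60) + 2·P(p > 0.60).

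Reproducing the plan's own cohorts of 3:
- 0/3 at 100 mg: 250 mg (plan: 250).
- Then 0, 1, 2, 3 DLTs at 250 mg: 300, 250, 200, 150 mg (plan: 300, 250, 200, 100).
- Then, after 0/3 at 250 mg, 0, 1, 2, 3 DLTs at 300 mg: 300, 300, 250, 250 mg (plan: the same).

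The one mismatch is 3/3 at 250 mg. There, maximising the target probability under the overdose limit gives the plan's 100 mg.

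On this model, a true 1/3 at 250 mg recorded as 0/3 changes the recommendation from 250 to 300 mg. A true 2/3 recorded as 1/3 changes it from 200 to 250 mg. At the first 300 mg cohort, recording 0/3 instead of 1/3 changes nothing at that step. With the same prior fitted to bridging data alone at 250 mg, 0/3 gives 300 and 1/3 gives 250; 0/6 and 1/6 both give 300, and 2/6 gives 250. So a missed DLT moves the dose by one 50 mg step in some positions and not in others.

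**5. Chance of recording a DLT, over an assumed range.** Let f be the share of DLTs that only a Day 15 chemistry sample would catch. The documents give no value for f. At a true DLT rate of 30%, the middle of the 25–35% target interval, with 3 patients:

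P(at least one recorded) = 1 − (1 − 0.30·(1 − f))³

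| f (assumed) | 0 | 10% | 25% | 50% |
|---|---|---|---|---|
| P | 0.657 | 0.611 | 0.535 | 0.386 |

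If all DLTs are hematologic, f = 0.

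**The case against.** A reader might infer that laboratory DLTs in general go unsought after Day 8. The documents do not support that. Day 15 hematology is kept, and Section 1.4 names thrombocytopenia and neutropenia as the main DLTs in the earlier idasanutlin solid tumor study. The expected DLTs are therefore tested identically.

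A reader might also infer a 50 mg upward shift in the rituximab dose. That figure comes from the Regimen A illustration. Section 3.1.2.3 promises only a similar model for the bridging cohorts and does not give its prior. Nothing in the documents says how likely a miss is.

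The remaining class is narrow. Idasanutlin is given on Days 1–5 and has a half-life of about 1 day (Section 1.3.3.1), and the Day 8 sample is kept. Under Section 5.3.5.5 an asymptomatic laboratory value counts as an adverse event only if it leads to a treatment change or intervention or is judged clinically significant, so some missed values would not have been DLTs. Section 5.1.3.5 asks for electrolyte monitoring during treatment, without fixing days. Unscheduled tests can be done, all safety data are reviewed before each dose decision, and clinical judgment overrides the model. All of this stands. It limits the size of the effect.

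The footnotes could be read as contradictory, since r asks for chemistry "within 24 hours prior to Days 8 and 15 of Cycle 1" on the very cell that t restricts. But r sets times and t sets the population, so they can be read together.

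The last objection is that Day 15 chemistry is a pre-infusion check, because obinutuzumab is infused on Cycle 1 Day 15 and rituximab is not. This does not fit the table. Day 8 chemistry is kept for rituximab patients, who receive no infusion that day, and Day 15 chemistry is kept for obinutuzumab patients after Cycle 1, when they are infused only on Day 1.

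**Conclusion.** The point holds for chemistry-based DLTs only. In the DLT window of the rituximab bridging cohort these have no scheduled test for about 18–21 days after Day 8, against a longest gap of about 11–14 days in the obinutuzumab cohorts. These figures assume nominal visit days and the 72-hour pre-cycle window.

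The exposure is confined to abnormalities that arise after Day 8 and resolve before about Day 26. How often that would happen cannot be derived from the documents, and it could be negligible. The direction does not depend on the frequency: a missed DLT makes a higher idasanutlin dose look more acceptable, in a cohort that begins at the obinutuzumab MTD and may go above it. The difference in ascertainment is unexplained and easily removed. This is a cheap improvement to the design; it does not invalidate the dose finding.

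**What to change.** In Appendix 2, remove footnote t from the Cycle 1 Day 15 serum chemistry cell for dose-escalation patients, so that the chemistry panel is run on the Day 15 draw already scheduled for hematology. Chemistry in the rituximab bridging cohort's DLT window would then match that of the Regimen A obinutuzumab cohorts. If the sponsor prefers to keep the difference, the protocol should state why.

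The cost is one additional local chemistry panel per bridging patient, with no extra visit. Later cycles and the expansion phase need not change for this purpose.

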### Schedule of Activities for Patients with DLBCL (cont.)

treatment. After this period, the Sponsor should be notified if the investigator becomes aware of any serious adverse event that is believed to be related to prior study treatment (see Section 5.6). An exception is made for Grade 3–4 infections (related and unrelated) *in patients who received obinutuzumab*, which should be reported until up to 2 years after the last dose of *obinutuzumab*. The investigator should follow each adverse event until the event has resolved to baseline grade or better, the event is assessed as stable by the investigator, the patient is lost to follow-up, or the patient withdraws consent. Every effort should be made to follow all serious adverse events considered to be related to any of the study treatment components or trial-related procedures until a final outcome can be reported.

- ii The screening PET-CT scan must be performed within 35 days prior to Day 1 of Cycle 1.
- jj Perform only for patients who have received at least two cycles of induction treatment.
- kk CT scan of the neck (if clinically indicated), chest, abdomen and pelvis. If contrast is medically contraindicated (e.g., patients with contrast allergy or impaired renal clearance), MRI scans of the chest, abdomen, and pelvis (and neck, if clinically indicated) and a non-contrast CT scan of the chest may be performed. Combined PET/CT scanners may be used to collect diagnostic CT scans, but only according to the technical guidelines in the imaging manual. Screening CT scan must be performed within 35 days prior to Day 1 of Cycle 1.
  - ll *Perform within 7 days prior to Day 1 of Cycle 3.*
  - mmm *Perform 4 months after initiation of consolidation treatment.*
  - nn Perform a CT scan 3 and 6 months after EOI visit, and every 6 months thereafter.
  - oo Bone marrow biopsy and aspirate must be performed within approximately 3 months prior to Day 1 of Cycle 1.
  - pp For patients with bone marrow involvement at screening, a repeat assessment will be performed at *the EOI, during consolidation, or at the EOC whenever there is radiologic evidence of a complete response or if clinically indicated (e.g., if there is clinical suspicion of progressive disease in the bone marrow with no radiologic evidence of progression). Additional bone marrow assessments may be performed at the discretion of the investigator.*
  - qq *For patients with bone marrow involvement at screening, a repeat assessment will be performed at EOI if there is radiologic evidence of a complete response.*
  - rr Refer to Section 4.3.2.3 and Section 4.3.2.5 for details on dosing and schedule.
  - ss *Regimen will be defined based on available safety, tolerability, PK, and PD data.*

**Appendix 3**  
**Schedule of Pharmacokinetic and Pharmacodynamic (MIC-1) Assessments for Obinutuzumab *or***  
***Rituximab and Idasanutlin in Regimen A***

Study Visit		Serum Obinutuzumab Pharmacokinetic Sample a	Serum Rituximab Pharmacokinetic Sample a	Plasma Idasanutlin Pharmacokinetic/Serum MIC-1 Sample b
Dose-Escalation Phase (Induction Treatment) (28-Day Cycles)				
Cycle 1	Day 1 c	Pre-infusion any time prior the first dose that day ; 30 (±10) minutes after end of infusion	Pre-infusion any time prior the first dose that day ; 30 (±10) minutes after end of infusion	Pre-administration any time prior the first dose that day 6 hr (±20 min) post idasanutlin administration
	Day 5	—		Prior to idasanutlin administration ( within 1 hr prior to dose ) 2 hours (±10 min) post-idasanutlin administration 4 hours (±10 min) post-idasanutlin administration 6 hours (±20 min) post-idasanutlin administration
Cycle 2	Day 1	Pre-infusion ( within 5 hr prior to dose ); 30 (±10) minutes after end of obinutuzumab infusion	Pre-infusion ( within 5 hr prior to dose )	Pre-administration ( within 1 hr prior to dose ) 6 hr (±20 min) post idasanutlin administration
	Day 5	—		(If patient is in clinic) Pre-administration ( within 1 hr prior to dose ) 6 hours (±20 min) post-idasanutlin administration

**Appendix 3**  
**Schedule of Pharmacokinetic and Pharmacodynamic (MIC-1) Assessments for Obinutuzumab or Rituximab and Idasanutlin in Regimen A (cont.)**

Study Visit		Serum Obinutuzumab Pharmacokinetic Sample a	Serum Rituximab Pharmacokinetic Sample a	Plasma Idasanutlin Pharmacokinetic/Serum MIC-1 Sample b
Dose-Escalation Phase (Induction Treatment) (28-Day Cycles)				
Cycle 4	Day 1	Pre-infusion (within 5 hr prior to dose); 30 (±10) minutes after end of obinutuzumab infusion	Pre-infusion (within 5 hr prior to dose)	Pre-administration (within 1 hr prior to dose) 6 hours (±20 min) post-idasanutlin administration
	Day 5	—		(If patient is in clinic) Pre-administration (within 1 hr prior to dose) 6 hours (±20 min) post-idasanutlin administration
Cycle 6	Day 1	Pre-infusion (within 5 hr prior to dose); 30 (±10) minutes after end of obinutuzumab infusion	Pre-infusion (within 5 hr prior to dose); 30 (±10) minutes after end of obinutuzumab infusion	—

**Appendix 3**  
**Schedule of Pharmacokinetic and Pharmacodynamic (MIC-1) Assessments for Obinutuzumab or Rituximab and Idasanutlin in Regimen A (cont.)**

Study Visit	Serum Obinutuzumab Pharmacokinetic Sample a	Serum or Rituximab Pharmacokinetic Sample a	Plasma Idasanutlin Pharmacokinetic/Serum MIC-1 Sample b	
Expansion Phase (Induction Treatment; 28-Day Cycles)				
Cycle 1	Day 1 c	Pre-infusion any time prior the first dose that day ; 30 (±10) minutes after end of infusion d	Pre-infusion any time prior the first dose that day ; 30 (±10) minutes after end of infusion c	Pre-administration any time prior the first dose that day 6 hr (±20 min) post idasanutlin administration
	Day 5			Prior to idasanutlin administration ( within 1 hr prior to dose ) 2 hours (±10 min) post-idasanutlin administration 4 hours (±10 min) post-idasanutlin administration 6 hours (±20 min) post-idasanutlin administration
Cycle 2	Day 1	Pre-infusion ( within 5 hr prior to dose ); 30 (±10) minutes after end of obinutuzumab infusion	Pre-infusion ( within 5 hr prior to dose )	Pre-administration ( within 1 hr prior to dose ) 6 hr (±20 min) post idasanutlin administration
	Day 5			(If patient is in clinic) Prior to idasanutlin administration ( within 1 hr prior to dose ) 6 hours (±20 min) post-idasanutlin administration

**Appendix 3**  
**Schedule of Pharmacokinetic and Pharmacodynamic (MIC-1) Assessments for Obinutuzumab or Rituximab and Idasanutlin in Regimen A (cont.)**

Study Visit		Serum Obinutuzumab Pharmacokinetic Sample a	Serum or Rituximab Pharmacokinetic Sample a	Plasma Idasanutlin Pharmacokinetic/Serum MIC-1 Sample b
Expansion Phase (Induction Treatment; 28-Day Cycles)				
Cycle 4	Day 1	Pre-infusion (within 5 hr prior to dose); 30 (±10) minutes after end of obinutuzumab infusion	Pre-infusion (within 5 hr prior to dose)	Pre-administration (within 1 hr prior to dose) 6 hr (±20 min) post idasanutlin administration
	Day 5			(If patient is in clinic) Prior to idasanutlin administration (within 1 hr prior to dose) 6 hours (±20 min) post-idasanutlin administration
Cycle 6	Day 1	Pre-infusion (within 5 hr prior to dose); 30 (±10) minutes after end of obinutuzumab infusion	Pre-infusion (within 5 hr prior to dose); 30 (±10) minutes after end of obinutuzumab infusion	

